1. INTRODUCTION

1.1 Study Disease

The most common site of metastatic disease in Ewing sarcoma is the lung. The standard management of pulmonary metastases continues to include whole-lung radiotherapy. Although there are reports advocating the use of whole-lung radiotherapy, this approach has not been shown in randomized trials to improve survival [1, 2.] Localized Ewing sarcoma is curable with radiotherapy doses of 54-60 Gy, however whole-lung doses are limited because of lung toxicity. Patients who relapse after whole-lung radiotherapy also have few curative options. An alternative to whole-lung radiotherapy is stereotactic body radiotherapy (SBRT). SBRT can provide sustained control of tumor in the lung by delivering a tumoricidal dose while limiting dose to the normal lung. Similarly, the most common site of metastatic disease for Wilms and other primary pediatric renal tumors is the lung. Whole lung radiotherapy is used in some children with metastatic renal tumors. However, for those who had non-metastatic disease but relapse in the lung following completion of therapy, the efficacy of whole lung radiotherapy is unproven.

1.2 Rationale

SBRT is a well studied and commonly used method of conforming the radiation dose to the target volume in order to spare normal surrounding tissues. By doing so, doses to the target can be increased without causing excessive toxicity to surrounding tissues. SBRT is being used to treat adults with small inoperable lung cancers [3-5]. SBRT has been shown to be effective and well-tolerated.

Several regimens have been used and are summarized in the table below along with results of local control, follow-up and risk of grade 3 or greater toxicity. The table below was used at the American Association of Medical Dosimetrists (AAMD) annual meeting in Minneapolis in June 2010.

Authors	Sample Size	Total Dose/# of Fractions (fx)	Local Control	Follow-up (mos)	≥ Grade 3 Toxicity
Uematsu et al ⁶	50	50-60 Gy/5-10 fx	94%	60	0.0%
Onishi et al ⁷	251	18-75 Gy/1-22 fx	86%	38	5.4%
Nagata et al ⁸	45	48 Gy/4 fx	98%	30	0.0%
Timmerman et al ⁹	37	60-66 Gy/3 fx	95%	24	5.4%
Baumann et al ¹⁰	138	30-48 Gy/2-4 fx	88%	33	10.1%*
Zimmermann et al ¹¹	68	37.5 Gy/3 fx	88%	36	3.0%
McGarry et al12	47	54-72 Gy/3 fx	87%	15	-
Xia et al ¹³	43	50 Gy/10 fx	95%	36	2.3%
*Some of the treated lincreased risk of treatm		in location, not peripheral, athough	the report does not	clarify whether a central	tumor location led to

SBRT has not routinely been used in the treatment of pulmonary metastases from Ewing sarcoma or from other malignancies in children, though there have been many studies published on its use in pulmonary metastases from adult cancers. Stereotactic radiotherapy to the brain has been used since 1992 to treat pediatric brain tumors and there is increasing interest in using this highly conformal technology in children [6].

2. OBJECTIVES

2.1 Study Design

This is a Phase I/II study. The purpose of this study is to find the lowest dose level with an acceptable safety profile and efficacy in this population. Therefore, the phase I and phase II designs will be run sequentially. Dose escalation in phase I does not go all the way to the MTD before moving to the phase II portion. If the dose being tested is found to be effective dose escalation will not continue. There are two cohorts that will use the same study design. One cohort will include patients with Wilms tumors or other primary renal tumors, and the other will include patients with Ewing sarcoma or rhabdomyosarcoma. Different dose levels will be used in the two cohorts, with non-renal tumor patients beginning at dose level 2 and renal tumor patients beginning at dose level 1. The two cohorts will be enrolling patients independently and simultaneously.

2.2 Primary Objectives

- 2.2.1 The primary aim of the Phase I portion is to determine the tolerability and safety of stereotactic body radiotherapy for pulmonary metastases in pediatric patients with Ewing sarcoma, rhabdomyosarcoma or Wilms tumor and other primary renal tumors. (See 11.1 for definitions.)
- 2.2.2 The primary objective of the Phase II portion is to evaluate disease response at 6 weeks post SBRT in this patient population. Response will be defined according to RECIST criteria.

2.3 Secondary Objectives

- 1. To determine the feasibility of SBRT in the pediatric population (including tolerability)
- 2. To document the safety of the treatment
- 3. To determine rate of relapse elsewhere in the lung
- 4. Best overall response

3. PARTICIPANT SELECTION

3.1 Eligibility Criteria

- 1. Diagnosis of Ewing sarcoma, rhabdomyosarcoma, osteosarcoma, non-rhabdomyosarcoma soft tissue sarcoma, Wilms tumor or other primary renal tumor (including clear cell and rhabdoid)
- 2. Age ≤21 years
- 3. Must be capable of treatment without general anesthesia
- 4. Lesion size 4 mm 3 cm

5. Subjects who have lesions within 2 cm of central structures*, will be eligible on a case-by-case basis

*Tumor within or touching the zone of the proximal bronchial tree, defined as a volume 2 cm in all directions around the proximal bronchial tree (carina, right and left main bronchi, right and left upper lobe bronchi, intermedius bronchus, right middle lobe bronchus, lingular bronchus, right and left lower lobe bronchi).

- 6. Pulmonary metastases found at relapse (does not have to be first relapse); no more than 3 lesions per hemi-thorax will be treated but other lesions in the lung may be present
- 7. Greater than 5 weeks from doxorubicin at the time of consent, with radiation to be initiated no less than 6 weeks from doxorubicin
- 8. Informed consent/assent
- 9. Life expectancy > 3 months
- 10. Pulmonary function FEV₁ ≥ 50% of predicted
- 11. Concurrent immunotherapy is allowed

3.2 Exclusion Criteria

- 1. Prior whole-lung or hemi-thorax irradiation of greater than 12 Gy received less than 6 months prior to consent (focal radiotherapy to the thorax is not an exclusion)
- 2. Lesion larger than 3 cm in diameter
- 3. Patients for whom surgery would be deemed appropriate rather than radiotherapy.

3.3 Inclusion of Women and Minorities

Females, minorities and other underrepresented populations are at risk to develop Ewing sarcoma and the other included malignancies and we will enroll any eligible patient in such groups. There is no reason to suspect any differential effect of this treatment. The eligibility criteria will not differentially affect the enrollment of these populations.

4. PRETREATMENT EVALUATIONS/MANAGEMENT

Eligible patients will be registered with the DF/HCC Office of Data Quality (ODQ). Registration must occur prior to initiation of therapy. Any participant not registered to the protocol before treatment begins will be deemed ineligible and registration denied. A member of the study team will confirm eligibility.

5. REGISTRATION PROCEDURES

5.1 General Guidelines for DF/HCC and DF/PCC Institutions

Institutions will register eligible participants in the Clinical Trials Management System (CTMS) OnCore. Registrations must occur prior to the initiation of protocol therapy.

Any participant not registered to the protocol before protocol therapy begins will be considered ineligible and registration will be denied.

An investigator will confirm eligibility criteria and a member of the study team will complete the protocol-specific eligibility checklist.

Following registration, participants may begin protocol therapy. Issues that would cause treatment delays should be discussed with the Overall Principal Investigator (PI). If a participant does not receive protocol therapy following registration, the participant's registration on the study must be canceled. Registration cancellations must be made in OnCore as soon as possible.

5.2 Registration Process for DF/HCC and DF/PCC Institutions

5.3 DF/HCC Standard Operating Procedure for Human Subject Research Titled Stereotactic Body Radiotherapy (SBRT) for Pulmonary Metastases in Ewing Sarcoma, Rhabdomyosarcoma, and Wilms Tumors (SOP #: REGIST-101) must be followed. General Guidelines for Other Participating Institutions

N/A

5.4 Registration Process for Other Participating Institutions

N/A

5.5 Stratification

Patients will be stratified into two groups by diagnosis: Wilms/Renal tumors are Cohort 1, Ewing sarcoma /rhabdomyosarcoma are Cohort 2

6. RADIATION THERAPY

6.1 Dose Specifications: 3D Conformal Radiotherapy (3DCRT) or IMRT

- 6.1.1 Treatment simulation: The patient will undergo simulation (treatment planning) in a standard stereotactic immobilization device. The simulation will be done using 4DCT to account for respiratory motion. A free-breathing CT scan will also be performed using 2.5-mm slices. Abdominal compression will be used if the tumor moves more than 1 cm with respiratory motion. This approach is the standard protocol for SBRT at our institution.
- 6.1.2 Contours: The tumor nodule or nodules will be contoured
 - 6.1.2.1 Internal tumor volume (ITV): gross tumor plus margin for internal motion.
 - 6.1.2.2 Planning target volume (PTV): will be ITV plus 5 mm

6.1.2.3 Organs at risk will be defined by the physician and/or the treatment planner:

- Total lung: total lung volume-ITV
- Heart: Defined from apex to first slice of great vessels
- Spinal cord
- Chest wall
- Skin
- Ribs abutting tumor
- Esophagus: defined 5 cm above and below PTV
- Proximal bronchial tree: defined from inferior 2 cm of trachea to lobar bronchi, to point of bifurcation into segments
- Brachial plexus

6.1.2.4 Dose Level 1 will be the starting dose for patients with Wilms/Renal tumor. Dose Level 2 will be the starting dose for patients with Ewing sarcoma/Rhabdomyosarcoma (non-renal). SEE APPENDIX: A.

Treatment will be delivered over 1-2 weeks. Delivery of hypofractionated radiotherapy (i.e., using a small number of fractions) makes it challenging to determine normal-tissue dose constraints. However, we will use very conservative critical-structure dose limits based on those used in published experience in SBRT in adults. See Appendix B for UTSW Dose Constraints.

6.1.2.5 Dose Levels for each target lesion are as follows:

Dose level 1 - 8 Gy x 3 Dose level 2 - 10 Gy x 3 Dose level 3 - 12 Gy x 3

Non-renal tumor dose escalation scheme: Three participants with non-renal tumors will be treated starting at dose level 2. If no dose-limiting toxicities (DLTs, see definitions in 6.2) are seen, that cohort will move on to the phase II portion of the study. If one DLT occurs at the initial dose level, then 3 more patients will be accrued to that cohort. If no further DLTs occur in those 3 patients treated at the initial dose level, then that cohort will move on to the phase II portion of the study. In the phase II portion, if the efficacy criteria are not met, three more patients will be enrolled at the next dose level. Dose will be escalated to the next dose level (3) for the next three patients. If one DLT, an additional three patients will be enrolled at that current dose level. If two or three DLTs, no dose escalation will occur; if this is at the starting dose level 2, dose will be deescalated to the next lower dose level for the next three patients, down to a minimum of dose level 1. If three patients are treated at dose level 2, three more at dose level 3, and there are still no DLTs, the dose will be held at level 3 for all additional non-renal tumor patients.

Renal tumor dose escalation scheme: Three participants with renal tumors will

be treated starting at dose level 1. If no dose-limiting toxicities (DLTs, see definitions in 6.2) are seen, that cohort will move on to the phase II portion of the study. If one DLT occurs at the initial dose level, then 3 more patients will be accrued to that cohort. If no further DLTs occur in those 3 patients treated at the initial dose level, then that cohort will move on to the phase II portion of the study. In the phase II portion, if the efficacy criteria are not met, three more patients will be enrolled at the next dose level. Dose will be escalated to the next dose level (2) for the next three patients. If one DLT, an additional three patients will be enrolled at that current dose level. If two or three DLTs, no dose escalation will occur; if this is at the starting dose level 1 (the lowest dose level), the study will be terminated. If three patients are treated at dose level 2, three more at dose level 3, and there are still no DLTs, the dose will be held at level 3.

6.1.2.6 Dose-escalation (please refer to Dose Schema section 6.1.2.5): The Phase I and Phase II portions will be done sequentially. If a dose level does not meet the safety criteria (none of three or no more than one out of six develops a DLT), and the next lower dose level does not meet the Phase II pre-specified criteria for efficacy, the study will be terminated. If two or more DLTs are observed at the starting dose level, the SBRT dose will be de-escalated to the next lower dose level; if this happens at dose level 1 (the lowest dose level), the study will be terminated.

The same Phase I/II design applies to both cohorts, Wilms and sarcoma patients, separately, except for the starting dose level in the Phase I portion. There are 3 dose levels (8, 10 and 12 Gy x 3) in this study. Patients with Wilms tumor or other renal tumors will start at dose level 1 (8 Gy x 3) and dose escalation will stop for this cohort at dose level 3 (12 Gy x 3). Ewing sarcoma and rhabdomyosarcoma patients will start at dose level 2 (10 Gy x 3).

6.1.2.7 Stopping rules: If two or more DLTs are observed at the starting dose level, the SBRT dose will be de-escalated to ther next lower dose level; if this happens at dose 1 (the lowest dose level), the study will be terminated.

6.2 Dose-limiting toxicities (DLTs)

DLTs are toxicities experienced between the start of the stereotactic radiotherapy and 6 months after radiotherapy. DLTs will be graded according to the CTEP active version of the National Cancer Institute's (NCI) Common Terminology Criteria for Adverse Events (CTCAE), located at:

http://ctep.cancer.gov/protocolDevelopment/electronic applications/ctc.htm.

The current version is CTCAE v4.0.

For this study, DLTs are defined as follows: The following grade 2 or higher toxicities:

- Myelitis
- Esophageal fistula, perforation, hemorrhage

The following grade 3 or higher toxicities considered to be a direct result of therapy:

- Pneumonitis
- Pericarditis, pericardial effusion
- Esophageal necrosis, stenosis, ulcer
- Dyspnea

The following grade 4 toxicities:

- Esophagitis
- Pericardial tamponade
- Pulmonary toxicity excluding infectious pneumonia
- Skin toxicity
- Hemoptysis/pulmonary hemorrhage

All grade 5 toxicities, including:

- Pulmonary toxicity including pneumonitis
- Excluding infectious pneumonia

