6.3 Toxicities and Adverse Events

6.3.1 Toxicities

6.3.1.1 All patients will be seen weekly by their treating radiation oncologist or coinvestigators (pediatric oncologist) while undergoing therapy. The following toxicities are expected and listed according to their likelihood and whether they are immediate or long term.

Evaluation of toxicity. All participants will be evaluable for toxicity from the time of their first treatment. Evaluation will be by the radiation oncology physician or by the patient's pediatric oncologist by physical examination and testing as indicated in the study calendar. Patients will be seen by the radiation oncologist for each treatment to assess toxicities and adverse events.

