7. OTHER THERAPIES

If systemic anti-cancer treatment is urgently required during the two weeks of study treatment, the subject will be removed from the study and replaced. However, patients will be allowed to receive concurrent immunotherapy.

During the Phase I portion, if clinically indicated, systemic therapy can be given and the subject will remain evaluable for the phase I (toxicity) portion. Surgery (other than to index lesions) will be allowed. These patients will be scored as unevaluable for response assessment.

During the Phase II portion, if systemic therapy is needed prior to the 6 week post-treatment assessment time, that subject but will be scored as UNEVALUABLE for response assessment but will be followed for toxicity. Surgery (other than to index lesions) is allowed if clinically indicated and the subject will remain evaluable.

However, if the reason for non-protocol surgery or chemotherapy is disease worsening of the index lesions, those patients would be scored as disease progression

Patients may receive Decadron orally prior to each fraction of radiotherapy per physician discretion.

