11 STATISTICAL CONSIDERATIONS

11.1 Study Design/Endpoints

A 3+3 study design will be used in the Phase I portion and patients will enter the study in sets of three for each cohort. For a given dose level, if none of three patients experiences a DLT, this dose level will move forward to the Phase II portion. However, if one patient experiences a DLT among the first three patients at any dose level, three more patients will be treated at that dose level. The dose level will enter the Phase II portion if no further DLT is observed following observation period of 6 months from treatment completion of third patient in the cohort. If a DLT is observed in any of the three additional patients, this dose level will not move forward to the Phase II portion and the dose will be de-escalated to the next lower level. If two or more patients experience a DLT among the first 3 patients, dose de-escalation will ensue, if applicable, without further testing of that dose level in the phase II portion. The table below shows the probability of entering the phase II portion for a dose level under different true DLT rates.

True DLT rate	5%	10%	15%	20%	30%	40%
Probability of entering phase II	0.97	0.91	0.81	0.71	0.49	0.31

Once a dose level enters the Phase II portion, a two-stage design will be used to evaluate efficacy. The first stage will accrue seven patients, including the patients enrolled at the same dose level in the Phase I portion. If at least two responses are observed among the seven patients, additional eight patients will be entered. If five or more responses are observed among the fifteen patients, there will be no further dose escalation and this dose level will be considered tolerable and effective for this patient population. With this design, the Phase II portion has 90% power to test the response rate of 50% vs. 20% based on a 0.14 level one-sided exact binomial test. The probability of stopping early is 0.58 if the true response rate is 20%; whereas if the true response rate is 50%, this probability is 0.06.

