If a dose level examined in the Phase II portion does not meet the pre-specified criteria for efficacy, the next higher dose level will start in the Phase I portion until a dose level that meets both Phase I and Phase II criteria for safety and efficacy is found. If a dose level does not meet the safety criteria (none of three or no more than one out of six develops a DLT), and the next lower dose level does not meet the Phase II pre-specified criteria for efficacy, the study will be terminated. If two or more DLTs are observed at the starting dose level, the SBRT dose will be de-escalated to the next lower dose level; if this happens at dose level 1 (the lowest dose level), the study will be terminated. The same Phase I/II design applies to both cohorts, renal tumor (cohort 1) and Ewing patients (cohort 2), separately, except for the starting dose level in the Phase I portion.

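### The 3+3 rule counts DLTs over 6 months but has no evaluability or replacement rule for patients who die of disease or are lost earlier, which tilts it toward passing a dose level

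*Combined protocol and SAP*

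**What the plan says.** - **Window.** Section 6.2: "DLTs are toxicities experienced between the start of the stereotactic radiotherapy and 6 months after radiotherapy".
- **Entry.** Section 3.1 admits patients with pulmonary metastases at relapse and requires "Life expectancy > 3 months".
- **Evaluability.** Section 6.3.1: "All participants will be evaluable for toxicity from the time of their first treatment".
- **Decision rule.** Section 11.1: "if none of three patients experiences a DLT, this dose level will move forward to the Phase II portion". With one DLT in the first three, three more patients are treated. The section restates the safety criterion as "none of three or no more than one out of six develops a DLT".
- **Waiting time.** In the branch with one DLT, section 11.1 lets the level proceed if no further DLT is seen "following observation period of 6 months from treatment completion of third patient in the cohort".
- **Replacement.** Section 7 covers one case: if urgent systemic anti-cancer treatment is needed during the two treatment weeks, "the subject will be removed from the study and replaced". Otherwise, in Phase I, "systemic therapy can be given and the subject will remain evaluable for the phase I (toxicity) portion".
- **Operating characteristics.** Section 11.1 prints the probability of entering Phase II as 0.97, 0.91, 0.81, 0.71, 0.49 and 0.31 at true DLT rates of 5, 10, 15, 20, 30 and 40%.

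**The concern.** The Phase I question is whether a DLT occurs within 6 months, and a patient can meet the survival criterion while expected to live little more than half that time. Someone who dies of tumour or is lost at month 3 is evaluable under section 6.3.1, has not experienced a DLT, and is outside the section 7 replacement rule. If the count is applied literally, that patient takes one of three or six slots as a non-event with half the window unseen.

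The unseen half matters for this treatment. Section 6.3.1.3 lists shortness of breath, heart inflammation, spinal cord injury and fatal lung inflammation as late toxicities, and these correspond to DLT terms in section 6.2. With only three patients, one unobserved slot is a third of the evidence.

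A level that passes goes on to stage 1 of Phase II. Stage 1 has seven patients including those from Phase I, so passing commits 7 − 6 = 1 to 7 − 3 = 4 further patients. Eight more follow only if at least two responses are seen in the seven.

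**Working it through.** **1. Reproduce the printed table.** A level passes with 0 DLTs in 3, or with 1 in the first 3 and 0 in the next 3. For a per-patient DLT probability p:

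P(enter) = (1−p)³ + 3p(1−p)² × (1−p)³ = (1−p)³ + 3p(1−p)⁵

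For p = 5, 10, 15, 20, 30, 40% this gives 0.9734, 0.9061, 0.8138, 0.7086, 0.4943, 0.3093, which matches the print at every rate. The formula takes each patient's 6-month DLT status as known.

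**2. Look for a rule that closes the gap.**
- The observation period in section 11.1 is calendar time from the third patient's treatment completion. It does not require each patient to be alive and assessed throughout.
- The replacement rule in section 7 covers only the two treatment weeks.
- Section 6.2 counts grade 5 toxicities, which covers toxic deaths but not deaths from tumour.
- Early death from malignant disease appears in section 9 only as a response category.

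**3. Let early leavers count as having no DLT.** Two inputs are assumptions, not in the documents: q, the share of patients who leave at month 3, and f, the share of DLTs that appear by month 3. The observed DLT probability becomes

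p* = p[(1−q) + fq]

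Example with p = 0.30, q = 1/3, f = 0.5: p* = 0.30 × (0.6667 + 0.1667) = 0.25, and P(enter) = 0.75³ + 3 × 0.25 × 0.75⁵ = 0.4219 + 0.1780 = 0.60.

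P(enter) at a true DLT rate of 30% (printed 0.49):

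| f | q = 1/6 | q = 1/3 | q = 1/2 |
|---|---|---|---|
| 0.75 | 0.52 | 0.55 | 0.57 |
| 0.50 | 0.55 | 0.60 | 0.65 |
| 0.25 | 0.57 | 0.65 | 0.74 |

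At a true rate of 40% (printed 0.31), the corners are 0.34 (q = 1/6, f = 0.75) and 0.60 (q = 1/2, f = 0.25).

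**4. Try a different leaving pattern.** With exponential survival and DLT times uniform over 6 months (both assumed), P(enter) at 30% is 0.55 if median survival is 24 months (16% dead by 6 months), 0.59 if 12 months (29% dead) and 0.67 if 6 months (50% dead). The direction is the same and the size similar.

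**5. Check what replacement does to the table.** If early leavers without a DLT are replaced and those with one are kept, the DLT probability per filled slot is

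p′ = p(1−q+fq) / [p(1−q+fq) + (1−q)(1−p)]

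With p = 0.30, q = 1/3, f = 0.5: p′ = 0.25 / (0.25 + 0.4667) = 0.349, and P(enter) is about 0.40, below the printed 0.49. With p = 0.10 and the same q and f: p′ = 0.0833 / (0.0833 + 0.6) = 0.122, and P(enter) = 0.87, against 0.91. Replacement therefore does not restore the printed table. It moves the rule to the cautious side.

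**The case against.** The strongest reply is that the plan does wait: section 11.1 has a 6-month observation period, so the safety decision was meant to see out the window. That stands as evidence of intent, and a reader should not infer that the plan ignores follow-up. But the sentence sits in the one-DLT branch and fixes when to look, not who counts.

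A second reply is that no section says in words that an early disease death is DLT-free, and that the evaluability sentence in 6.3.1 may only define who enters the toxicity tables. This too is partly right. The DLT-free status is a consequence of applying the rules together, and an investigator might handle it otherwise. The plan does not tell them to.

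Third, the size rests on assumptions. The 3-month figure is an entry minimum, not expected survival. Section 6.3.1.2 lists lung inflammation as an immediate toxicity, so many DLTs could fall early; with f = 0.75 and q = 1/6 the rise is only from 0.49 to 0.52. This stands, and it is why a range is given.

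A reader might also infer three stronger things that the documents do not support:
- *That the printed table is wrong.* It is arithmetically correct under complete observation.
- *That this gap alone lets an unsafe level through.* A level with a 30% DLT rate already passes with probability 0.49 under full follow-up; the gap adds to an existing risk.
- *That passing commits 9 to 12 more patients* (15 − 6 to 15 − 3). That is the total only if stage 2 opens.

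There are partial safeguards: SAE reporting within 24 hours through 6 months (section 6.3.2.3.2) and quarterly review by the monitoring committee (section 12.3). Neither defines who is evaluable for the DLT count.

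**Conclusion.** The gap is real. The plan has no definition of a DLT-evaluable patient and no rule for an incomplete window, and the literal count treats early disease deaths and losses as non-events. The direction is certain, because a truncated window can only miss DLTs. The size is not known. Under the assumed ranges (one sixth to one half leaving at month 3, 25% to 75% of DLTs seen by then), entry to Phase II at a true 30% DLT rate is 0.52 to 0.74 rather than 0.49. If nearly all patients are followed for 6 months, the effect is negligible. The point should be fixed because it bears on the main safety decision and is cheap to close. The lack of a 6-month death rate, the small number of patients committed before the stage 1 check, and the existing oversight keep it short of a bar to proceeding.

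**What to change.** In sections 6.2 and 11.1, define a patient as DLT-evaluable for the 3+3 count only if he or she had a DLT at any time in the window or was observed DLT-free for the full 6 months. Replace any other patient for that count only. Keep replaced patients in all toxicity tables and in the Phase II response count, and report how many there were.

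Beside the table in section 11.1, state that it assumes every patient's 6-month DLT status is fully observed. Add that, with early leavers under the replacement rule, the entry probabilities are somewhat lower: for example, about 0.40 instead of 0.49 at a true 30% rate if one third leave at month 3 and half of DLTs appear by then.

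The text change is a few sentences. The real cost is time. At the 3 renal patients per year expected in section 11.2, one replacement takes about 12/3 = 4 months to accrue plus 6 months to observe; at 5 per year in the other cohort, 12/5 = 2.4 months plus 6. Total accrual need not usually rise, because a replacement treated at the same level can be one of the seven stage 1 patients.

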6.3.1.3 Late Toxicities

Common (>20%)

• Scarring of the lung not requiring treatment (permanent)

Uncommon (10-20%)

- Shortness of breath (permanent)
- Skin dryness in the treatment field (permanent)
- Inflammation of the heart (duration weeks)
- Chest wall pain

Rare (<10%)

- Inflammation of the muscles of the chest wall (duration weeks)
- Scarring of the lung requiring treatment (permanent)
- Rib fracture
- Tumors caused by radiotherapy (lifelong)

Extremely rare (<5%)

- Spinal cord injury (permanent)
- Fatal inflammation of the lung

6.3.1.4 Clinical discretion may be used in managing radiotherapy-related side effects.

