APPENDIX B UTSW DOSE CONSTRAINTS

	Timmerman, 12-2008		
Volume	Volume Max (Gy)	Max Point Dose (Gy)	Endpoint (≥Grade 3)
<0.2 cc	8 Gy	10 Gy	neuritis
		9 Gy	hearing loss
		15 Gy	cranial neuropathy
		14 Gy	myelitis
	10 Gy	14 Gy	myelitis
subvolume		1	
			neuritis
			neuropathy
			stenosis/fistula
			neuropathy
			pericarditis
			aneurysm
<4 cc	10.5 Gy	20.2 Gy	stenosis/fistula
<0.5 cc	12.4 Gy	13.3 Gy	stenosis with atelectasis
<1 cc	22 Gy	30 Gy	Pain or fracture
<10 cc	23 Gy	26 Gy	ulceration
<10 cc	11.2 Gy	12.4 Gy	ulceration/fistula
<5 cc	11.2 Gy	12.4 Gy	ulceration
<10 cc	9 Gy		
<5 cc	11.9 Gy	15.4 Gy	enteritis/obstruction
<20 cc	14.3 Gy	18.4 Gy	colitis/fistula
<20 cc	14.3 Gy	18.4 Gy	proctitis/fistula
<15 cc	11.4 Gy	18.4 Gy	cystitis/fistula
<3 cc	14 Gy	34 Gy	impotence
<10 cc	14 Gy		necrosis
<2/3 volume	10.6 Gy		malignant hypertension
Critical Volume (cc)	Critical Volume Dose Max (Gy)		Endpoint (≥Grade 3)
1500 cc	7 Gy		Basic Lung Function
1000 cc	7.4 Gy		Pneumonitis
700 cc	9.1 Gy		Basic Liver Function
200 cc	8.4 Gy	***************************************	Basic renal function
	<0.5 cc <0.35 cc <1.2 cc <1.2 cc <10% of subvolume <5 cc <5 cc <5 cc <15 cc <10	<0.2 cc	Volume Volume Max (Gy) Max Point Dose (Gy) <0.2 cc

Three Fractions				Timmerman
Serial Tissue	Volume	Volume Max (Gy)	Max Point Dose (Gy)	Endpoint (≥Grade 3)
Optic Pathway	<0.2 cc	15.3 Gy (5.1 Gy/fx)	17.4 Gy (5.8 Gy/fx)	neuritis
Cochlea			17.1 Gy (5.7 Gy/fx)	hearing loss
Brainstem (not medulla)	<0.5 cc	18 Gy (6 Gy/fx)	23.1 Gy (7.7 Gy/fx)	cranial neuropathy
Spinal Cord and medulla	<0.35 cc <1.2 cc	18 Gy (6 Gy/fx) 12.3 Gy (4.1 Gy/fx)	21.9 Gy (7.3 Gy/fx)	myelitis
Spinal Cord Subvolume (5- 6 mm above and below level treated per Ryu)	<10% of subvolume	18 Gy (6 Gy/fx)	21.9 Gy (7.3 Gy/fx)	myelitis
Cauda Equina	<5 cc	21.9 Gy (7.3 Gy/fx)	24 Gy (8 Gy/fx)	neuritis
Sacral Plexus	<5 cc	21 Gy (7 Gy/fx)	24.6 Gy (8.2 Gy/fx)	neuropathy
Esophagus*	<5 cc	17.7 Gy (5.9 Gy/fx)	25.2 Gy (8.4 Gy/fx)	stenosis/fistula
Brachial Plexus	<3 cc	20.4 Gy (6.8 Gy/fx)	24 Gy (8 Gy/fx)	neuropathy
Heart/Pericardium	<15 cc	24 Gy (8 Gy/fx)	30 Gy (10 Gy/fx)	pericarditis
Great vessels	<10 cc	39 Gy (13 Gy/fx)	45 Gy (15 Gy/fx)	aneurysm

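### Section 6.2 omits brachial plexus injury from the DLT list, so a treatment-related grade 3-4 plexopathy within 6 months would not count at the Phase I gate

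*Combined protocol and SAP*

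**What the plan says.** Section 6.2 counts toxicities from the start of SBRT to 6 months after it, in four tiers:

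- Grade 2 or higher: myelitis; esophageal fistula, perforation or hemorrhage.
- "The following grade 3 or higher toxicities considered to be a direct result of therapy": pneumonitis; pericarditis or pericardial effusion; esophageal necrosis, stenosis or ulcer; dyspnea.
- Grade 4: esophagitis, tamponade, pulmonary toxicity, skin toxicity, hemoptysis or pulmonary hemorrhage.
- Grade 5: all toxicities, apart from infectious pneumonia.

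Only the grade 5 tier is open-ended.

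The gate refers back to this list. For each cohort, section 6.1.2.5 says of the first three patients: "If no dose-limiting toxicities (DLTs, see definitions in 6.2) are seen, that cohort will move on to the phase II portion of the study". Sections 6.1.2.6 and 11.1 apply the same rule: no DLT in three patients, or at most one in six. A level that passes can reach fifteen patients, and with five or more responses "this dose level will be considered tolerable and effective for this patient population".

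Section 6.1.2.3 includes "Brachial plexus" among the organs at risk. In the three-fraction table of Appendix B, the plexus row allows 20.4 Gy to less than 3 cc and a maximum point dose of 24 Gy, with neuropathy of grade 3 or higher as the endpoint to be avoided.

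**The concern.** The protocol plans radiation around the plexus in order to avoid a severe neuropathy, but does not count that neuropathy if it happens. None of the listed terms covers it: myelitis is a cord injury, and the skin, pulmonary and dyspnea terms do not describe a nerve injury.

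Rarity does not explain the gap. Section 6.3.1.3 puts spinal cord injury in its rarest category, under 5%, yet myelitis counts from grade 2. Esophageal injury is absent from the expected toxicities in section 6.3.1, yet it fills three DLT bullets. The documents give no reason for leaving the plexus out.

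At stake is what happens after one such event in the first three patients. As written, with no listed DLT, the count is 0/3 and the level goes directly to Phase II. If the event counted, three more patients would be treated and observed at that level first. The patients are aged 21 or under, and each decision rests on three to six of them.

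**Working it through.** **1. The plan's own gate figures.** With true DLT rate p, a level passes with 0/3, or with 1/3 followed by 0/3:

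f(p) = (1-p)^3 + 3p(1-p)^2 × (1-p)^3 = (1-p)^3 + 3p(1-p)^5

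For p = 5, 10, 15, 20, 30 and 40% this gives 0.973, 0.906, 0.814, 0.709, 0.494 and 0.309. The table in section 11.1 shows 0.97, 0.91, 0.81, 0.71, 0.49 and 0.31, so it is reproduced.

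**2. Dose against limit.** The three levels total 3 × 8 = 24 Gy, 3 × 10 = 30 Gy and 3 × 12 = 36 Gy. The plexus point limit is 24 Gy. The prescription equals the limit at level 1 and exceeds it at levels 2 and 3, so the limit matters for any lesion near the plexus.

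**3. Rates (assumed).** No document gives a rate for plexopathy. The nearest anchor is the table in section 1.2, which gives "results of local control, follow-up and risk of grade 3 or greater toxicity" in adult series. Seven of the eight series report toxicity, from 0 to 10.1%. The weighted mean is

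(50×0 + 251×5.4 + 45×0 + 37×5.4 + 138×10.1 + 68×3.0 + 43×2.3) / 632 = 3251.9 / 632 = 5.1%.

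That covers all toxicity of grade 3 or higher, in adults, over 24-60 months. I assume a listed DLT rate d of 3% or 5% and a plexopathy rate q of 1% or 2%, independent of each other, so the combined rate is p = 1 - (1-d)(1-q).

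**4. Effect of counting plexopathy.** The chance of expansion is that of exactly one event in the first three patients, 3p(1-p)^2.

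| d | q | p | Probability of entering Phase II, f(p) | Chance of expansion |
|---|---|---|---|---|
| 3% | 0 (as written) | 0.0300 | 0.990 | 8.5% |
| 3% | 1% | 0.0397 | 0.983 | |
| 3% | 2% | 0.0494 | 0.974 | 13.4% |
| 5% | 0 (as written) | 0.0500 | 0.973 | 13.5% |
| 5% | 1% | 0.0595 | 0.963 | |
| 5% | 2% | 0.0690 | 0.952 | 17.9% |

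The probability of entering Phase II falls by 0.7 to 1.0 points at q = 1% and by 1.6 to 2.1 points at q = 2%. At q = 2% the chance of expansion rises by 4.9 points (d = 3%) or 4.4 points (d = 5%).

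A pessimistic case, q = 5% on top of d = 10%, gives 0.906 falling to 0.824. Its combined rate of 14.5% is above the worst series in the section 1.2 table (10.1%), so it is an outer bound.

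**5. How often the gap would matter.** The chance that at least one of three patients has a plexopathy is 1 - 0.99^3 = 3.0% at q = 1% and 1 - 0.98^3 = 5.9% at q = 2%. The chance of two or more in three at 2% is 3(0.02^2)(0.98) + 0.02^3 = 0.12%.

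**The case against.** The strongest defense is that such an injury would not pass unseen. Serious events within 6 months go to the principal investigator and the IRB (6.3.2.3.2). Plexopathy is not among the toxicities in section 6.3.1, so on that list it is unexpected, although the consent document could not be checked. Section 12.3 names unexpected events of grade 2 or higher among the data that the DSMC may receive. Section 11.4 tabulates toxicities by dose level, and the Appendix B limits are there to prevent the injury. All of this stands and reduces the risk. None of it changes the 0/3 or 1/6 count, so holding the level would depend on discretion.

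Three stronger readings are tempting, and the documents do not support them.

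- *Rib and chest wall injuries are an equal omission.* The protocol does contour "Ribs abutting tumor" and the chest wall, and section 6.3.1.3 expects rib fracture (under 10%) and "Chest wall pain" (10-20%). But it lists both as late effects, with frequencies for any grade, so many may fall after 6 months and the severe share is unknown. The right grade is also debatable: if grade 3 chest wall pain were a DLT, two such events at level 1 would end the study.
- *A neurotoxic dose is likely to be declared tolerable.* Two plexopathies in three patients has a probability of about 0.1% at an assumed 2%, and the gate moves by only 1-2 points.
- *The plexus will be overdosed because the prescription meets or exceeds its limit.* The prescription applies to the target and the limit to the plexus. They conflict only for a lesion close to it.

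**Conclusion.** The point holds for the brachial plexus and is worth an amendment. That plexopathy below grade 5 does not count follows from the text alone and needs no assumption. The size does rest on assumptions: a rate of 1-2%, listed DLTs at 3-5%, and independence. On these, counting plexopathy lowers the probability of entering Phase II by about 1-2 percentage points. A rate of 2% for this one injury would be a large part of the 5.1% total in the adult series, which had longer follow-up than the DLT window, so the true shift may be smaller. The case therefore rests on having a fixed response to a rare, serious event when it occurs. It does not show that the gate is badly calibrated or that the section 11.1 table is wrong.

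**What to change.** In section 6.2, add one bullet, *Brachial plexopathy*, to the tier for grade 3 or higher events attributed to therapy. Apply it prospectively; rescoring patients already treated would change the gate after their outcomes are known. Leave the 6-month window, the other grade thresholds and the 0/3 or 1/6 rule as they are.

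The amendment is one line, and adverse events are already graded and recorded (6.3.2.2). The main cost is the 4-5 point higher chance of a three-patient expansion at an assumed 2%. At the accrual rates in section 11.2, an expansion takes 3/3 = 1.0 year in the renal cohort or 3/5 = 0.6 year (about 7 months) in the non-renal cohort, plus the 6-month observation. If the level then passes, those patients count toward the seven in the first stage of Phase II. As with any DLT, two events at a starting level force de-escalation, or termination at level 1.

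The investigators may also consider rib fracture, chest wall pain or chest wall necrosis, choosing the grade on clinical grounds. With the window unchanged, later events would still be missed.
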